12.2 Plasma PK Endpoints

The PK parameters based on data collected on Day 10 following IV administration and Week 10 following SC administration will be derived, using Phoenix WinNonlin, Version 8.1 or higher. The PK parameter derivation is based on actual sampling times and includes imputation of the values below the lower limit of quantification (BLQ) and missing data will be conducted in accordance to [CSL SOP PK-GDL-01](#), Guideline on the Conduct of Non-compartmental Pharmacokinetic Analyses, CSL Behring which gives guidance on how to derive PK parameters in the presence of missing data.

Definition of derived PK Parameter:

Term	Definition
AUC _{0-t}	Area under the concentration time curve from time point zero to the last quantifiable time point.
C _{max}	The maximum (peak) observed C1-INH level.
T _{max}	The time to reach C _{max} .

Term	Definition
C_{trough}	Trough C1-INH, collected prior to the next infusion.

12.3 Summary of C1-INH Antigen and Functional Activity Plasma Concentrations

The handling and imputation of BLQ values for PK parameters derivation is described in PK-GDL-01, Guideline on the Conduct of Non-compartmental Pharmacokinetic Analyses, CSL Behring. The imputation rules below will be used for summary statistics of C1-INH antigen and functional activity plasma concentrations. The summaries will be given by sampling time point (planned time points) and treatment group for the PK Analysis Set.

- The sampling time of pre-dose samples relative to dosing will be set to zero.
- Any BLQ in the listing of individual concentrations will be set to missing.
- Set any pre-dose BLQ to zero for summaries.
- Set any BLQ occurring in the profile or at the end of the profile to missing and exclude missing values from the calculation of the means.
- Calculate mean concentrations at any individual time point if at least 50% of the individual values are available (ie are quantifiable and not missing) at this time point otherwise report as “not calculated (NC)”.

Summary statistics for concentration-time data will include number of observations, mean, standard deviation, coefficient of variation (CV)%, minimum, median and maximum.

A by-subject listing of C1-INH antigen and functional activity plasma concentration data will support the summaries.

12.4 Summary of C1-INH PK Parameters

PK parameters of C_{max} , AUC_{0-t} , C_{trough} and for C1-INH antigen and functional activity will be summarized by treatment group for the PK Analysis Set by descriptive statistics with parameter of n, arithmetic mean, SD, CV% ($CV\% = 100 * \text{standard deviation} / \text{mean}$), minimum, Q25, median, Q75, and maximum.

T_{max} will be summarized by descriptive statistics with parameter of n, minimum, Q25, median, Q75, and maximum.

A by-subject listing of C1-INH PK parameters will be provided.

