10.3.5 Pharmacokinetics Analyses

Blood samples will be collected for the assessment of C1-esterase inhibitor antigen concentrations and C1-esterase inhibitor functional activity at designated timepoints. C1-esterase inhibitor functional activity will be determined by a validated assay.

The observed C1-esterase inhibitor antigen concentrations and functional activity will be summarized by time, route of administration, and treatment subgroup (placebo vs C1-INH).

The parameters AUC_{0-t} and C_{max} will be estimated, if feasible, using non-compartmental PK analyses in the subset of ~20 subjects who have more frequent, sequential PK sampling at the Day 10 Visit and the Week 11 Visit.

In addition, population PK analyses may also be conducted and reported separately.

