4.3 Study Treatments

Dose and Dosing Regimen

A summary of dose and dosing regimen is shown in Table 4.

Table 4 Summary of dose and dosing regime

Timeframe	Intravenous Administration	Subcutaneous Administration
Treatment Period 1: The Day 1 Visit to the Day 13 Visit ^a	60 IU/kg C1-INH	Not applicable
Treatment Period 1: The Day 14 Visit to the Week 12 2 nd Visit ^a	Not Applicable	60 IU/kg C1-INH
Treatment Period 2: Week 13 to the Week 38 Visit ^b	Not Applicable	60 IU/kg C1-INH OR 0.12 mL/kg Placebo
Re-treatment Period: The Retreatment Day 1 Visit to the Retreatment Week 26 Visit. ^c	Not Applicable	60 IU/kg C1-INH OR 0.12 mL/kg Placebo

IV = intravenous; SC = subcutaneous

^a Treatment Period 1 is open-label and each subject will receive C1-INH. C1-INH (60 IU/kg) will be administered IV to each subject over the first 13 days of Treatment Period 1 for a total of 5 doses. Thereafter, C1-INH (60 IU/kg twice weekly) will be administered SC to each subjects for the remainder of Treatment Period 1. The first dose of randomized investigational product will be administered to responders at the Week 13 Visit.

^b Treatment Period 2 is blinded and subjects will be randomized 1:1 to treatment with investigational product (C1-INH [60 IU/kg] or placebo) subcutaneously twice weekly.

^c Retreatment Period(s) are blinded and subjects will receive the same investigational product treatment assignment as received during Treatment Period 2.

Note: Week 13 is the final visit of Treatment Period 1 for non-responders and the first visit of Treatment Period 2 for responders.

Treatment Period 1

C1-INH will be administered to all subjects during Treatment Period 1 in an open-label manner. Five doses of C1-INH will be administered intravenously to subjects at the Day 1, 4, 7, 10, and 13 Visits. Intravenous C1-INH will be administered at the study site during site visits. Subcutaneous C1-INH will be administered every 3 to 4 days (ie, twice weekly) beginning at the Day 14 Visit and for the remainder of Treatment Period 1. Subcutaneous C1-INH is required to be administered at the study site during site visits, but at other times may instead be administered at home by a medical professional ((eg, a home visit nurse) or by the subject under the supervision of a medical professional.

Treatment Period 2

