4.4 Randomization Procedures and Blinding

Randomization Procedures

All subjects will receive open-label C1-INH during Treatment Period 1. Subjects who are eligible for Treatment Period 2 will be assigned to either continued C1-INH or matched placebo in accordance with a computer-generated randomization list. Investigational product assigned in Treatment Period 2 will be allocated on a 1:1 ratio. The randomization will be stratified on the following 2 factors:

- Donor Specific Antibodies (DSA): sensitized prior to transplantation versus de novo. De novo is defined as the development of DSA after transplantation. In the case of both sensitized and de novo, the subject will be considered sensitized for stratification purposes.
- AMR severity: severe versus non-severe (ie all other severities). Severe AMR is defined as new onset oliguria (< 400 cc / 24 hours) or anuria with the current episode of AMR.

Therefore, there will be a total of 4 strata (2 factors, 2 levels per factor). The randomization will be permuted block within each stratum. Treatment assignment will be determined centrally. The randomization list will be generated and managed by the study's interactive response technology (IRT) external service provider.

The study database will be locked once all the randomized subjects currently in the study complete week 38 visit and re-treatment period as described in [Section 3](#). The study will be unblinded for final analysis of the primary efficacy endpoint.

Maintaining the Blind

Treatment Period 1 is open-label. Treatment Period 2 is double-blind. During Treatment Period 2, the blind will be maintained for investigational site staff, including investigators, subjects, and CSL.

Emergency Unblinding

In emergency situations involving the safety of the subject, the investigator may break the blind using the IRT system. The reason for unblinding the randomization code must be fully documented. Emergency unblinding will be performed using the IRT. Steps for navigating the IRT for emergency unblinding are defined in the IRT manual.

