7.2 Treatment Descriptors

The following treatment group descriptor will be used on all applicable displays:

Treatment Group		Order of Treatment Groups
Code	Description	
A	Placebo	1
B	C1-INH	2

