12.1 PK Sampling Schedule

Blood samples will be taken for measurement of C1-INH antigen concentrations and C1-INH functional activity at the following time points of Day 10 of Treatment Period 1: pre-dose, 0 minutes (start of C1-INH infusion), 15 minutes, 3, 8, 24, and 72 hours after start of infusion and at Week 11 visit (Treatment Period 1) at time points of: pre-dose, 0 minutes (time of C1-INH injection), 24, 48, and 72 hours after injection. PK samples will be drawn in a subset of subjects.

Summary statistics will be provided by nominal (planned) time points.

Concentration data excluded from the derivation of PK parameters will be omitted from summaries and will be flagged with an asterisk in the relevant data listings, with a footnote to indicate that these values have been omitted from subsequent analyses.

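### SAP 12.4 groups PK parameters by randomized treatment although they are measured in open-label TP1, before randomization, when every subject is on C1-INH

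*SAP*

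**What the plan says.** SAP 12.4 states that Cmax, AUC0-t and Ctrough for C1-INH antigen and "functional activity will be summarized by treatment group for the PK Analysis Set by descriptive statistics". It names no route, visit or overall column. The separate sentence on Tmax gives statistics but no grouping. SAP 12.3 has a similar rule for concentrations: "The summaries will be given by sampling time point (planned time points) and treatment group for the PK Analysis Set".

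SAP 7.2 supplies the groups: "The following treatment group descriptor will be used on all applicable displays", followed by two codes, Placebo and C1-INH. There is no open-label, non-randomized or total group.

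On the source of the parameters, SAP 12.2 says: "The PK parameters based on data collected on Day 10 following IV administration and Week 10 following SC administration will be derived". SAP 12.1 places the SC profile "at Week 11 visit (Treatment Period 1) at time points of: pre-dose, 0 minutes (time of C1-INH injection), 24, 48, and 72 hours after injection". Protocol 10.3.5 estimates AUC0-t and Cmax "in the subset of ~20 subjects who have more frequent, sequential PK sampling at the Day 10 Visit and the Week 11 Visit".

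On treatment at that time, SAP 4.4 says "All subjects will receive open-label C1-INH during Treatment Period 1", and SAP 4.3 says the same: "C1-INH will be administered to all subjects during Treatment Period 1 in an open-label manner".

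The secondary endpoint in SAP 4.2.2.2 (Table 2) and Protocol 2.2.2 (Table 8) is Cmax and AUC0-t of functional activity after IV and after SC dosing. It is defined by route, not by arm.

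**The concern.** A table of drug exposure should be grouped by what the subject was receiving when the samples were drawn. Here the grouping variable is an assignment made afterwards, and only for some of the subjects. Three consequences follow from a literal reading:

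- A Placebo column would contain Cmax and AUC values measured under C1-INH dosing. A reader of the study report could take them for exposure on placebo.
- Subjects with a valid profile who did not respond in TP1 have no defined place in the table.
- The contrast that the endpoint asks for, IV against SC, is not specified, while one that carries no pharmacokinetic meaning at these visits is.

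Route matters by the protocol's own figures: Protocol 3.3.2 gives simulated peaks of 2.3-fold above normal for IV and 1.7-fold for SC. The endpoint is also still live. The visible entries in SAP 5, which lists analyses withdrawn after termination, do not include the PK parameters.

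**Working it through.** The plan states no figure for this table, so there is nothing to reproduce. The check is mainly a comparison of sections, followed by one illustration.

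**1. Timing**

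| Event | When | Source |
|---|---|---|
| IV profile | Day 10, TP1 | SAP 12.1, Protocol Table 6 |
| SC profile | Week 11, TP1 (SAP 12.2 says Week 10) | SAP 12.1, Protocol Table 6 |
| Responder status and randomization | Week 13 | Protocol 8.1.3.2, 8.5.3.14 |

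Both profiles precede randomization, and everyone is on C1-INH at both.

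**2. Who has a treatment group.** Only TP1 responders are randomized (Protocol 8.1.3.2). The PK Analysis Set (SAP 6.6) needs one C1-INH dose and one measurable level, so it includes subjects who were never randomized. SAP 12.4 uses that set but gives these subjects no group.

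**3. Whether the actual-treatment rule helps.** SAP 8.2.8 takes actual treatment from exposure data. Where actual and assigned treatment agree, the assigned label stands; it changes only if a different treatment was received throughout. A subject correctly given placebo in TP2 therefore keeps the Placebo label. A non-randomized subject has no assignment to compare.

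**4. How the SAP handles other TP1 output.** SAP 10.4 and 10.5 (TP1 eGFR and response) use the Run-in Safety set. SAP 10.20 (TP1 compliance) uses the same set and also splits TP1 compliance into IV and SC delivery. SAP 11 uses it for TP1 safety. Section 12.4 departs from this pattern.

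**5. Illustration of size.** Inputs: PK subset about 20 (Protocol 10.3.5); 60 randomized from N = 120, up to 175, in TP1 (Protocol 3.5). Assumptions not in the documents: the PK subset is randomized at the overall planned rate, the arms are equal in size, and the SD is the same in each.

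- Subjects with a group = 20 × 60/N
- Per arm = half of that
- SE ratio, one arm against all 20 combined = √(20 / n per arm)

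| N | With a group | Without | Per arm | SE ratio |
|---|---|---|---|---|
| 120 | 20 × 60/120 = 10 | 10 | 5 | √(20/5) = 2.0 |
| 175 | 20 × 60/175 = 6.9 | 13.1 | 3.4 | √(20/3.43) = 2.4 |

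**The case against.** The best defence is that this is a layout ambiguity in a descriptive table. SAP 7.2 limits its descriptors to applicable displays, and a programmer who follows the SAP's other TP1 outputs might present one open-label column. SAP 4.2.1.3 and 7.3 rule out formal testing. SAP 12.4 plans no standard error or confidence interval. By-subject listings are promised in SAP 10.10 and 12.4, so a pooled summary could be rebuilt. For concentrations, Protocol 10.3.5 itself calls for a placebo versus C1-INH split alongside time and route.

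Much of this stands, and it limits the point. It does not remove it: 12.4 expressly invokes treatment group, and the SAP defines only two.

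A reader might infer more than the documents support:

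- *That the plan drops non-randomized subjects.* No section excludes them. Their column is undefined.
- *That IV and SC are pooled, so the endpoint is not produced.* SAP 12.2 derives parameters separately at two visits, each with one route, and nothing in 12.4 combines them. The split is unnamed, not abolished.
- *That precision is irretrievably lost.* The individual values are listed.
- *That the loss is worse at the 13 subjects randomized by termination (SAP 3).* The actual size of the PK subset is not given, so this cannot be checked.
- *That SAP 12.3 is wrong throughout.* Treatment grouping is right for post-randomization concentrations. Only the TP1 time points share the problem.

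**Conclusion.** The point holds as a defect in a stated grouping rule. Followed literally, SAP 12.4 with 7.2 labels C1-INH exposures as Placebo, leaves never-randomized PK subjects without a defined column, and does not name the route split on which the secondary endpoint is defined. This rests on the text alone.

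The size is illustrative. At the planned numbers, about 3 to 5 subjects per arm would stand in place of about 20 combined, with a standard error of a mean about 2.0 to 2.4 times larger. That depends on the assumed randomization rate and common SD; the realized figure is unknown. No hypothesis test and no primary result is affected. The point is worth correcting because the endpoint is still to be reported and the correction is cheap.

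**What to change.** - **SAP 12.4:** summarize the Day 10 IV and Week 11 SC parameters, including Tmax, separately by route, with all PK-subset subjects combined in one C1-INH column.
- **SAP 12.3:** present TP1 concentrations the same way. Keep treatment-group columns only for post-randomization samples (Weeks 16, 32 and 38, and Month 12).
- **Reconcile** Week 10 in SAP 12.2 with Week 11 in SAP 12.1, and the listing in SAP 10.10 with the summary in SAP 12.4.

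The cost is SAP wording and a table shell, with no new data or derivation. SAP 12.5 has the PK output pre-programmed on dummy data before database lock, so the shell should be settled before then. If the SAP can no longer be amended, the change can be recorded in the study report as a deviation, which SAP 7 provides for.

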12.5 Pharmacokinetic Analysis Data Flow

After database lock, PPD [REDACTED] will produce the SDTM domains. Domain PC will contain the C1-INH antigen concentrations and C1-INH functional activity concentrations. The PC domain along with domains VS, DM and EX will be provided by PPD [REDACTED]. PPD [REDACTED] Early Phase Services will derive the PK parameters and produce the PK parameter dataset in Excel format. From this, PPD [REDACTED] will produce the SDTM domain PP and eventually the analysis dataset.

Before database lock, PPD [REDACTED] will use dummy data for the PK parameters in domain PP to be able to pre-program the planned output.

13 CCI [REDACTED]

CCI [REDACTED]

16.1 Standardized MedDRA Query for Embolic and Thrombotic Events (Narrow) (SMQ Code: 20000081)

SMQ Name: Embolic and thrombotic events, arterial (SMQ)				SMQ Code:20000082
Preferred Term	Code	Level	Scope	Category
Acute aortic syndrome	10074337	PT	Narrow	A
Acute myocardial infarction	10000891	PT	Narrow	A
Amaurosis	10001902	PT	Narrow	A
Amaurosis fugax	10001903	PT	Narrow	A
Angioplasty	10002475	PT	Narrow	A
Aortic bypass	10057617	PT	Narrow	A
Aortic embolus	10002897	PT	Narrow	A
Aortic surgery	10061651	PT	Narrow	A
Aortic thrombosis	10002910	PT	Narrow	A
Aortogram abnormal	10057794	PT	Narrow	A
Arterectomy	10071026	PT	Narrow	A
Arterectomy with graft replacement	10003140	PT	Narrow	A
Arterial angioplasty	10081731	PT	Narrow	A
Arterial bypass occlusion	10077766	PT	Narrow	A
Arterial bypass operation	10056418	PT	Narrow	A
Arterial bypass thrombosis	10077765	PT	Narrow	A
Arterial graft	10061655	PT	Narrow	A
Arterial occlusive disease	10062599	PT	Narrow	A
Arterial revascularisation	10084482	PT	Narrow	A
Arterial stent insertion	10061657	PT	Narrow	A
Arterial therapeutic procedure	10052949	PT	Narrow	A
Arterial thrombosis	10003178	PT	Narrow	A
Arteriogram abnormal	10061659	PT	Narrow	A
Arteriogram carotid abnormal	10003195	PT	Narrow	A
Arteriotomy	10078636	PT	Narrow	A
Atherectomy	10063025	PT	Narrow	A
Atherosclerotic plaque rupture	10076604	PT	Narrow	A
Atrial appendage closure	10079735	PT	Narrow	A
Atrial appendage resection	10080843	PT	Narrow	A
Basal ganglia infarction	10069020	PT	Narrow	A

Preferred Term	Code	Level	Scope	Category
Basilar artery occlusion	10048963	PT	Narrow	A
Basilar artery thrombosis	10063093	PT	Narrow	A
Blindness transient	10005184	PT	Narrow	A
Brachiocephalic artery occlusion	10069694	PT	Narrow	A
Capsular warning syndrome	10067744	PT	Narrow	A
Carotid angioplasty	10071260	PT	Narrow	A
Carotid arterial embolus	10007684	PT	Narrow	A
Carotid artery bypass	10053003	PT	Narrow	A
Carotid artery occlusion	10048964	PT	Narrow	A
Carotid artery stent insertion	10066102	PT	Narrow	A
Carotid artery thrombosis	10007688	PT	Narrow	A
Carotid endarterectomy	10007692	PT	Narrow	A
Cerebellar artery occlusion	10053633	PT	Narrow	A
Cerebellar artery thrombosis	10008023	PT	Narrow	A
Cerebral artery embolism	10008088	PT	Narrow	A
Cerebral artery occlusion	10008089	PT	Narrow	A
Cerebral artery stent insertion	10081893	PT	Narrow	A
Cerebral artery thrombosis	10008092	PT	Narrow	A
Cerebral hypoperfusion	10065384	PT	Narrow	A
Cerebrovascular insufficiency	10058842	PT	Narrow	A
Cerebrovascular stenosis	10061751	PT	Narrow	A
Coeliac artery occlusion	10069696	PT	Narrow	A
Coronary angioplasty	10050329	PT	Narrow	A
Coronary arterial stent insertion	10052086	PT	Narrow	A
Coronary artery bypass	10011077	PT	Narrow	A
Coronary artery embolism	10011084	PT	Narrow	A
Coronary artery occlusion	10011086	PT	Narrow	A
Coronary artery reocclusion	10053261	PT	Narrow	A
Coronary artery surgery	10011090	PT	Narrow	A
Coronary artery thrombosis	10011091	PT	Narrow	A
Coronary endarterectomy	10011101	PT	Narrow	A
Coronary revascularisation	10049887	PT	Narrow	A
Coronary vascular graft occlusion	10075162	PT	Narrow	A
Embolia cutis medicamentosa	10058729	PT	Narrow	A
Embolism arterial	10014513	PT	Narrow	A
Endarterectomy	10014648	PT	Narrow	A
Femoral artery embolism	10068365	PT	Narrow	A
Hepatic artery embolism	10019635	PT	Narrow	A

Preferred Term	Code	Level	Scope	Category
Hepatic artery occlusion	10051991	PT	Narrow	A
Hepatic artery thrombosis	10019636	PT	Narrow	A
Hypothenar hammer syndrome	10063518	PT	Narrow	A
Iliac artery embolism	10021338	PT	Narrow	A
Iliac artery occlusion	10064601	PT	Narrow	A
Internal capsule infarction	10083408	PT	Narrow	A
Intra-aortic balloon placement	10052989	PT	Narrow	A
Intraoperative cerebral artery occlusion	10056382	PT	Narrow	A
Ischaemic cerebral infarction	10060840	PT	Narrow	A
Ischaemic stroke	10061256	PT	Narrow	A
Lacunar infarction	10051078	PT	Narrow	A
Leriche syndrome	10024242	PT	Narrow	A
Mesenteric arterial occlusion	10027394	PT	Narrow	A
Mesenteric arteriosclerosis	10065560	PT	Narrow	A
Mesenteric artery embolism	10027395	PT	Narrow	A
Mesenteric artery stenosis	10027396	PT	Narrow	A
Mesenteric artery stent insertion	10071261	PT	Narrow	A
Mesenteric artery thrombosis	10027397	PT	Narrow	A
Myocardial infarction	10028596	PT	Narrow	A
Myocardial necrosis	10028602	PT	Narrow	A
Ophthalmic artery thrombosis	10081144	PT	Narrow	A
Papillary muscle infarction	10033697	PT	Narrow	A
Penile artery occlusion	10068035	PT	Narrow	A
Percutaneous coronary intervention	10065608	PT	Narrow	A
Peripheral arterial occlusive disease	10062585	PT	Narrow	A
Peripheral arterial reocclusion	10069379	PT	Narrow	A
Peripheral artery angioplasty	10057518	PT	Narrow	A
Peripheral artery bypass	10072561	PT	Narrow	A
Peripheral artery occlusion	10057525	PT	Narrow	A
Peripheral artery stent insertion	10072562	PT	Narrow	A
Peripheral artery surgery	10082470	PT	Narrow	A
Peripheral artery thrombosis	10072564	PT	Narrow	A
Peripheral embolism	10061340	PT	Narrow	A
Peripheral endarterectomy	10072560	PT	Narrow	A
Popliteal artery entrapment syndrome	10071642	PT	Narrow	A
Post procedural myocardial infarction	10066592	PT	Narrow	A
Postinfarction angina	10058144	PT	Narrow	A
Precerebral artery occlusion	10036511	PT	Narrow	A

Preferred Term	Code	Level	Scope	Category
Precerebral artery thrombosis	10074717	PT	Narrow	A
Profundoplasty	10078867	PT	Narrow	A
Pulmonary artery occlusion	10078201	PT	Narrow	A
Pulmonary artery therapeutic procedure	10063731	PT	Narrow	A
Pulmonary artery thrombosis	10037340	PT	Narrow	A
Pulmonary endarterectomy	10072893	PT	Narrow	A
Pulmonary tumour thrombotic microangiopathy	10079988	PT	Narrow	A
Renal artery angioplasty	10057493	PT	Narrow	A
Renal artery occlusion	10048988	PT	Narrow	A
Renal artery thrombosis	10038380	PT	Narrow	A
Renal embolism	10063544	PT	Narrow	A
Retinal artery embolism	10038826	PT	Narrow	A
Retinal artery occlusion	10038827	PT	Narrow	A
Retinal artery thrombosis	10038831	PT	Narrow	A
Silent myocardial infarction	10049768	PT	Narrow	A
Spinal artery embolism	10049440	PT	Narrow	A
Spinal artery thrombosis	10071316	PT	Narrow	A
Splenic artery thrombosis	10074600	PT	Narrow	A
Splenic embolism	10068677	PT	Narrow	A
Stress cardiomyopathy	10066286	PT	Narrow	A
Subclavian artery embolism	10042332	PT	Narrow	A
Subclavian artery occlusion	10069695	PT	Narrow	A
Subclavian artery thrombosis	10042334	PT	Narrow	A
Thromboembolectomy	10064958	PT	Narrow	A
Thrombotic microangiopathy	10043645	PT	Narrow	A
Thrombotic thrombocytopenic purpura	10043648	PT	Narrow	A
Transient ischaemic attack	10044390	PT	Narrow	A
Truncus coeliacus thrombosis	10062363	PT	Narrow	A
Vascular pseudoaneurysm thrombosis	10078269	PT	Narrow	A
Vertebral artery occlusion	10048965	PT	Narrow	A
Vertebral artery thrombosis	10057777	PT	Narrow	A
Visual acuity reduced transiently	10047532	PT	Narrow	A

SMQ Name: Embolic and thrombotic events, venous (SMQ)		SMQ Code:20000084		
Preferred Term	Code	Level	Scope	Category
Aseptic cavernous sinus thrombosis	10084527	PT	Narrow	A
Axillary vein thrombosis	10003880	PT	Narrow	A
Brachiocephalic vein occlusion	10076837	PT	Narrow	A
Brachiocephalic vein thrombosis	10063363	PT	Narrow	A
Budd-Chiari syndrome	10006537	PT	Narrow	A
Catheterisation venous	10052698	PT	Narrow	A
Cavernous sinus thrombosis	10007830	PT	Narrow	A
Central venous catheterisation	10053377	PT	Narrow	A
Cerebral venous sinus thrombosis	10083037	PT	Narrow	A
Cerebral venous thrombosis	10008138	PT	Narrow	A
Compression garment application	10079209	PT	Narrow	A
Deep vein thrombosis	10051055	PT	Narrow	A
Deep vein thrombosis postoperative	10066881	PT	Narrow	A
Embolism venous	10014522	PT	Narrow	A
Hepatic vein embolism	10078810	PT	Narrow	A
Hepatic vein occlusion	10058991	PT	Narrow	A
Hepatic vein thrombosis	10019713	PT	Narrow	A
Homans' sign positive	10051031	PT	Narrow	A
Iliac vein occlusion	10058992	PT	Narrow	A
Inferior vena cava syndrome	10070911	PT	Narrow	A
Inferior vena caval occlusion	10058987	PT	Narrow	A
Jugular vein embolism	10081850	PT	Narrow	A
Jugular vein occlusion	10076835	PT	Narrow	A
Jugular vein thrombosis	10023237	PT	Narrow	A
Mahler sign	10075428	PT	Narrow	A
May-Thurner syndrome	10069727	PT	Narrow	A
Mesenteric vein thrombosis	10027402	PT	Narrow	A
Mesenteric venous occlusion	10027403	PT	Narrow	A
Obstetrical pulmonary embolism	10029925	PT	Narrow	A
Obstructive shock	10073708	PT	Narrow	A
Ophthalmic vein thrombosis	10074349	PT	Narrow	A
Ovarian vein thrombosis	10072059	PT	Narrow	A
Paget-Schroetter syndrome	10050216	PT	Narrow	A
Pelvic venous thrombosis	10034272	PT	Narrow	A
Penile vein thrombosis	10034324	PT	Narrow	A
Peripheral vein occlusion	10083103	PT	Narrow	A
Peripheral vein thrombus extension	10082853	PT	Narrow	A

Preferred Term	Code	Level	Scope	Category
Phlebectomy	10048874	PT	Narrow	A
Portal vein cavernous transformation	10073979	PT	Narrow	A
Portal vein embolism	10082030	PT	Narrow	A
Portal vein occlusion	10058989	PT	Narrow	A
Portal vein thrombosis	10036206	PT	Narrow	A
Portosplenomesenteric venous thrombosis	10077623	PT	Narrow	A
Post procedural pulmonary embolism	10063909	PT	Narrow	A
Post thrombotic syndrome	10048591	PT	Narrow	A
Postoperative thrombosis	10050902	PT	Narrow	A
Postpartum venous thrombosis	10036300	PT	Narrow	A
Pulmonary embolism	10037377	PT	Narrow	A
Pulmonary infarction	10037410	PT	Narrow	A
Pulmonary microemboli	10037421	PT	Narrow	A
Pulmonary thrombosis	10037437	PT	Narrow	A
Pulmonary vein occlusion	10068690	PT	Narrow	A
Pulmonary veno-occlusive disease	10037458	PT	Narrow	A
Pulmonary venous thrombosis	10037459	PT	Narrow	A
Renal vein embolism	10038547	PT	Narrow	A
Renal vein occlusion	10056293	PT	Narrow	A
Renal vein thrombosis	10038548	PT	Narrow	A
Retinal vein occlusion	10038907	PT	Narrow	A
Retinal vein thrombosis	10038908	PT	Narrow	A
Septic pulmonary embolism	10083093	PT	Narrow	A
SI QIII TIII pattern	10068479	PT	Narrow	A
Splenic vein occlusion	10068122	PT	Narrow	A
Splenic vein thrombosis	10041659	PT	Narrow	A
Subclavian vein occlusion	10079164	PT	Narrow	A
Subclavian vein thrombosis	10049446	PT	Narrow	A
Superior sagittal sinus thrombosis	10042567	PT	Narrow	A
Superior vena cava occlusion	10058988	PT	Narrow	A
Superior vena cava syndrome	10042569	PT	Narrow	A
Thrombophlebitis	10043570	PT	Narrow	A
Thrombophlebitis migrans	10043581	PT	Narrow	A
Thrombophlebitis neonatal	10043586	PT	Narrow	A
Thrombophlebitis superficial	10043595	PT	Narrow	A
Thrombosed varicose vein	10043605	PT	Narrow	A
Thrombosis corpora cavernosa	10067270	PT	Narrow	A
Transverse sinus thrombosis	10044457	PT	Narrow	A

Preferred Term	Code	Level	Scope	Category
Vena cava embolism	10047193	PT	Narrow	A
Vena cava filter insertion	10048932	PT	Narrow	A
Vena cava filter removal	10074397	PT	Narrow	A
Vena cava thrombosis	10047195	PT	Narrow	A
Venogram abnormal	10047209	PT	Narrow	A
Venoocclusive disease	10062173	PT	Narrow	A
Venoocclusive liver disease	10047216	PT	Narrow	A
Venous angioplasty	10077826	PT	Narrow	A
Venous occlusion	10058990	PT	Narrow	A
Venous operation	10062175	PT	Narrow	A
Venous recanalisation	10068605	PT	Narrow	A
Venous repair	10052964	PT	Narrow	A
Venous stent insertion	10063389	PT	Narrow	A
Venous thrombosis	10047249	PT	Narrow	A
Venous thrombosis in pregnancy	10067030	PT	Narrow	A
Venous thrombosis limb	10061408	PT	Narrow	A
Venous thrombosis neonatal	10064602	PT	Narrow	A
Visceral venous thrombosis	10077829	PT	Narrow	A

SMQ Name: Embolic and thrombotic events, vessel type unspecified and mixed arterial and venous (SMQ)				
SMQ Code:20000083				
Preferred Term	Code	Level	Scope	Category
Administration site thrombosis	10075968	PT	Narrow	A
Adrenal thrombosis	10075178	PT	Narrow	A
Angiogram abnormal	10060956	PT	Narrow	A
Angiogram cerebral abnormal	10052906	PT	Narrow	A
Angiogram peripheral abnormal	10057517	PT	Narrow	A
Antiphospholipid syndrome	10002817	PT	Narrow	A
Application site thrombosis	10076026	PT	Narrow	A
Arteriovenous fistula occlusion	10058562	PT	Narrow	A
Arteriovenous fistula thrombosis	10003192	PT	Narrow	A
Arteriovenous graft thrombosis	10053182	PT	Narrow	A
Artificial blood vessel occlusion	10078895	PT	Narrow	A
Atrial thrombosis	10048632	PT	Narrow	A
Basal ganglia stroke	10071043	PT	Narrow	A
Bone infarction	10049824	PT	Narrow	A
Brain stem embolism	10074422	PT	Narrow	A
Brain stem infarction	10006147	PT	Narrow	A
Brain stem stroke	10068644	PT	Narrow	A
Brain stem thrombosis	10062573	PT	Narrow	A
Cardiac ventricular thrombosis	10053994	PT	Narrow	A
Catheter site thrombosis	10079523	PT	Narrow	A
Cerebellar embolism	10067167	PT	Narrow	A
Cerebellar infarction	10008034	PT	Narrow	A
Cerebral congestion	10076929	PT	Narrow	A
Cerebral infarction	10008118	PT	Narrow	A
Cerebral infarction foetal	10008119	PT	Narrow	A
Cerebral ischaemia	10008120	PT	Narrow	A
Cerebral microembolism	10078311	PT	Narrow	A
Cerebral microinfarction	10083668	PT	Narrow	A
Cerebral septic infarct	10070671	PT	Narrow	A
Cerebral thrombosis	10008132	PT	Narrow	A
Cerebral vascular occlusion	10076895	PT	Narrow	A
Cerebrospinal thrombotic tamponade	10052173	PT	Narrow	A
Cerebrovascular accident	10008190	PT	Narrow	A
Cerebrovascular accident prophylaxis	10049165	PT	Narrow	A
Cerebrovascular disorder	10008196	PT	Narrow	A
Cerebrovascular operation	10051902	PT	Narrow	A

Preferred Term	Code	Level	Scope	Category
Choroidal infarction	10057403	PT	Narrow	A
Collateral circulation	10069729	PT	Narrow	A
Coronary bypass thrombosis	10059025	PT	Narrow	A
Device embolisation	10074896	PT	Narrow	A
Device occlusion	10064685	PT	Narrow	A
Device related thrombosis	10077455	PT	Narrow	A
Diplegia	10013033	PT	Narrow	A
Directional Doppler flow tests abnormal	10013048	PT	Narrow	A
Disseminated intravascular coagulation	10013442	PT	Narrow	A
Disseminated intravascular coagulation in newborn	10013443	PT	Narrow	A
Embolic cerebellar infarction	10084072	PT	Narrow	A
Embolic cerebral infarction	10060839	PT	Narrow	A
Embolic pneumonia	10065680	PT	Narrow	A
Embolic stroke	10014498	PT	Narrow	A
Embolism	10061169	PT	Narrow	A
Eye infarction	10083006	PT	Narrow	A
Fluorescence angiogram abnormal	10083087	PT	Narrow	A
Foetal cerebrovascular disorder	10053601	PT	Narrow	A
Gastric infarction	10084858	PT	Narrow	A
Graft thrombosis	10051269	PT	Narrow	A
Haemorrhagic adrenal infarction	10079902	PT	Narrow	A
Haemorrhagic cerebral infarction	10019005	PT	Narrow	A
Haemorrhagic infarction	10019013	PT	Narrow	A
Haemorrhagic stroke	10019016	PT	Narrow	A
Haemorrhagic transformation stroke	10055677	PT	Narrow	A
Haemorrhoids thrombosed	10019023	PT	Narrow	A
Hemiparesis	10019465	PT	Narrow	A
Hemiplegia	10019468	PT	Narrow	A
Heparin-induced thrombocytopenia	10062506	PT	Narrow	A
Hepatic infarction	10019680	PT	Narrow	A
Hepatic vascular thrombosis	10074494	PT	Narrow	A
Implant site thrombosis	10063868	PT	Narrow	A
Incision site vessel occlusion	10076839	PT	Narrow	A
Infarction	10061216	PT	Narrow	A
Infusion site thrombosis	10065489	PT	Narrow	A
Injection site thrombosis	10022104	PT	Narrow	A
Inner ear infarction	10070754	PT	Narrow	A
Instillation site thrombosis	10073625	PT	Narrow	A

Preferred Term	Code	Level	Scope	Category
Intestinal infarction	10022657	PT	Narrow	A
Intracardiac mass	10066087	PT	Narrow	A
Intracardiac thrombus	10048620	PT	Narrow	A
Lambl's excrescences	10083691	PT	Narrow	A
Medical device site thrombosis	10076145	PT	Narrow	A
Mesenteric vascular insufficiency	10027401	PT	Narrow	A
Mesenteric vascular occlusion	10074583	PT	Narrow	A
Microembolism	10073734	PT	Narrow	A
Monoparesis	10027925	PT	Narrow	A
Monoplegia	10027926	PT	Narrow	A
Optic nerve infarction	10030936	PT	Narrow	A
Pancreatic infarction	10068239	PT	Narrow	A
Paradoxical embolism	10066059	PT	Narrow	A
Paraneoplastic thrombosis	10079251	PT	Narrow	A
Paraparesis	10033885	PT	Narrow	A
Paraplegia	10033892	PT	Narrow	A
Paresis	10033985	PT	Narrow	A
Peripheral revascularisation	10053351	PT	Narrow	A
Pituitary infarction	10035092	PT	Narrow	A
Placental infarction	10064620	PT	Narrow	A
Pneumatic compression therapy	10059829	PT	Narrow	A
Portal shunt procedure	10077479	PT	Narrow	A
Post procedural stroke	10066591	PT	Narrow	A
Postpartum thrombosis	10077022	PT	Narrow	A
Prosthetic cardiac valve thrombosis	10063176	PT	Narrow	A
Prosthetic vessel implantation	10068628	PT	Narrow	A
Quadriparesis	10049680	PT	Narrow	A
Quadriplegia	10037714	PT	Narrow	A
Renal infarct	10038470	PT	Narrow	A
Renal vascular thrombosis	10072226	PT	Narrow	A
Retinal infarction	10051742	PT	Narrow	A
Retinal vascular thrombosis	10062108	PT	Narrow	A
Revascularisation procedure	10084091	PT	Narrow	A
Shunt occlusion	10040621	PT	Narrow	A
Shunt thrombosis	10059054	PT	Narrow	A
Spinal cord infarction	10058571	PT	Narrow	A
Spinal stroke	10082031	PT	Narrow	A
Splenic infarction	10041648	PT	Narrow	A

Preferred Term	Code	Level	Scope	Category
Splenic thrombosis	10074601	PT	Narrow	A
Stoma site thrombosis	10074515	PT	Narrow	A
Stroke in evolution	10059613	PT	Narrow	A
Strokectomy	10084735	PT	Narrow	A
Surgical vascular shunt	10058408	PT	Narrow	A
Testicular infarction	10043337	PT	Narrow	A
Thalamic infarction	10064961	PT	Narrow	A
Thrombectomy	10043530	PT	Narrow	A
Thromboangiitis obliterans	10043540	PT	Narrow	A
Thrombolysis	10043568	PT	Narrow	A
Thrombosis	10043607	PT	Narrow	A
Thrombosis in device	10062546	PT	Narrow	A
Thrombosis mesenteric vessel	10043626	PT	Narrow	A
Thrombosis prophylaxis	10043634	PT	Narrow	A
Thrombotic cerebral infarction	10067347	PT	Narrow	A
Thrombotic stroke	10043647	PT	Narrow	A
Thyroid infarction	10043742	PT	Narrow	A
Tumour embolism	10045168	PT	Narrow	A
Tumour thrombectomy	10081994	PT	Narrow	A
Tumour thrombosis	10068067	PT	Narrow	A
Ultrasonic angiogram abnormal	10061604	PT	Narrow	A
Ultrasound Doppler abnormal	10045413	PT	Narrow	A
Umbilical cord occlusion	10076714	PT	Narrow	A
Umbilical cord thrombosis	10071652	PT	Narrow	A
Vaccination site thrombosis	10076190	PT	Narrow	A
Vascular access site thrombosis	10078675	PT	Narrow	A
Vascular device occlusion	10080803	PT	Narrow	A
Vascular graft	10067740	PT	Narrow	A
Vascular graft occlusion	10049060	PT	Narrow	A
Vascular graft thrombosis	10069922	PT	Narrow	A
Vascular operation	10049071	PT	Narrow	A
Vascular stent insertion	10063382	PT	Narrow	A
Vascular stent occlusion	10077143	PT	Narrow	A
Vascular stent thrombosis	10063934	PT	Narrow	A

Preferred Term	Code	Level	Scope	Category
Vasodilation procedure	10058794	PT	Narrow	A
Vessel puncture site occlusion	10076838	PT	Narrow	A
Vessel puncture site thrombosis	10070649	PT	Narrow	A
Visual midline shift syndrome	10066856	PT	Narrow	A
SMQ Export: 23.1 - English 2/12/2020 8:42:53 PM				

